2.3 RANDOMIZATION AND MASKING

The randomization schedule will be generated by a biostatistician using simple random sampling. Participants will be randomized within center at the first visit. After all baseline assessments are completed, the delegated unmasked study coordinator will refer to the randomization scheme to assign each subject to one of the two study arms. All study participants who are randomized into the study will comprise the intent-to-treat population. Participants will be randomized into 1 of 2 different treatment arms.

The labeling differences between the lifitegrast and the vehicle will be known to only the unmasked coordinator. The unmasked coordinator will dispense the appropriate treatment to the subject. All drug dispensing and accountability will be done by an unmasked study coordinator so the investigator can remain masked.

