3 STUDY POPULATION

3.1 INCLUSION CRITERIA

In order to be eligible to participate in this study, an individual must meet all of the following criteria:

- 1. Subjects must read, understand and sign the Statement of Informed Consent
- 2. Subjects must be at least 18 years of age
- 3. Subjects must be habitual soft contact lens (CL) wearers, with a daily, weekly, bi- weekly or

- monthly replacement schedule
- 4. Habitual contact lenses must have a suitable fit as determined by the investigator
- 5. Subjects must report a history of dry eye symptoms, for which they have used rewetting drops or Artificial Tears (ATs) in the past 30 days
- 6. Subjects must be willing to discontinue the use of Artificial Tears (ATs) and rewetting drops for the duration of the study
- 7. Subjects must have a score of 12 or higher on the CLDEQ at baseline
- 8. Subjects must have at least 2 of the following signs of dry eye disease:
 - a. High tear osmolarity > 308mOsm/L, or a difference greater than 8 mOsm/L between eyes
 - b. Any corneal staining
 - c. Any bulbar conjunctival staining
 - d. Low TBUT (<10s)
 - e. Schirmer <10mm in either eye
- 9. Subjects must be able to read at least half of the 20/25 (via entrance Snellen visual acuity) or better in each eye in their current contact lens prescription.
- 10. Subjects currently wearing reusable contact lenses must be willing to use Clear Care solution for cleaning and disinfecting throughout the study.

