3.3 SAMPLE SIZE JUSTIFICATION

Assuming normality, we calculated the statistical power for various detectable effect sizes using unpaired t-test in a two-sided hypothesis test with a significance level, 0.05, where the ratio of sample size of 1:1 is assumed between study arms. **Table 1** shows that our sample size will have adequate power to detect listed effect size. For example, we will achieve 84% power to detect a standardized mean difference of 1.12 between two groups of a size of 15 for each, which corresponds to a difference of score change by 3 with standard deviations 3.2 and 2.0 for each group⁵. Up to 40 subjects will be enrolled with the goal of randomizing 30 subjects (15 per arm). This will allow for a 25% screen-failure rate. Note that for each

domain score and the overall score, the power is the same for each effect size since they are standardized, but the mean change corresponding to a given effect size differs.

Table 1

Sample size (N)	Unpaired t-test		
N1 vs. n2	Effect size 1	Power (%)	
15 vs. 15	1	75.3	
	1.12	84.4	
	1.2	87.5	

¹ standardized mean difference of 2 groups

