5 STATISTICS

The clinical characteristics of subjects including demographics and lens modality will be first summarized using descriptive statistics in mean \pm SD for continuous variables or % (counts) for categorical variables, with attention to assessing balance in these characteristics by study arms, and with assessment of the distribution of variables, relevant to the choice of statistical tests. For the continuous outcomes, we will conduct the Kolmogorov-Smirnov or the Shapiro-Wilk test to confirm normality of measurements prior to performing statistical analyses. Detection of outliers will be done using histograms, box-plots, normal plots and summary statistics. Where appropriate, logarithmic transformation will be further done.

All analyses will be conducted using the principle of "intent-to-treat" in which every participant is assumed to have received his/her assigned intervention, regardless of adherence. In order to assess for the significant difference between study arms for the primary outcomes of change in total score on the CLDEQ-8 after 8 weeks of treatment or continuous secondary outcomes (change in tear osmolarity), bivariate comparisons will be first conducted using t-tests. Alternatively Wilcoxon nonparametric counterpart will be used for continuous variables that deviate from normality. The forced choice questionnaire will be compared as a percentage of "yes" responses between the two groups by a two-sample test of proportion. These univariate analyses will be followed by multivariable regression methods for an adjustment of all other potential confounding variables such as baseline clinical and demographic characteristics that differ by study arms.

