Alternatively, we will use longitudinal linear models to analyze the difference of changes in total score between study arms from the baseline to the follow-up times across baseline, 2nd, 4th and 8th weeks (i.e., mixed-effects regression models with a random subject effect and GEE with exchangeable and independent correlations). The models will be specified with random intercepts and slopes such that a linear trajectory representing outcome will be compared between groups. Group (arm)-specific (as well as individual-level) intercepts and slopes over the period of follow-up will be included as random effects, while other covariates will be modeled as fixed effects. All models will be adjusted for other clinical or demographic confounders. Residual-based diagnostics will be used to evaluate validity of model assumptions. Two sided p-values <0.05 will be considered to be statistically significant. All statistical procedures were performed using R statistical package (www.R-project.org).

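### The primary CLDEQ-8 test is an unadjusted change-score comparison and no analysis names baseline CLDEQ-8 as a covariate, so a small, nearly free gain in precision is left unused

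*Combined protocol and SAP*

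**What the plan says.** Section 5 (Statistics) of the combined protocol and SAP sets out three layers of analysis for the primary outcome.

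- **First:** "bivariate comparisons will be first conducted using t-tests", or a Wilcoxon test where normality fails. No covariate enters.
- **Next:** "multivariable regression methods for an adjustment of all other potential confounding variables such as baseline clinical and demographic characteristics that differ by study arms".
- **Then, unranked:** "Alternatively, we will use longitudinal linear models to analyze the difference of changes in total score between study arms". Baseline is one of the four response times, intercepts are arm-specific, and on covariates the text says only "All models will be adjusted for other clinical or demographic confounders".

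Section 3.3 sizes the trial to match the first layer: "we calculated the statistical power for various detectable effect sizes using unpaired t-test in a two-sided hypothesis test".

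Baseline CLDEQ-8 is available for every randomised subject. The schedule in section 2.4 includes it at Visit 1. Section 3.1 makes it an entry criterion: "Subjects must have a score of 12 or higher on the CLDEQ at baseline". Section 2.3 places allocation after it: "After all baseline assessments are completed, the delegated unmasked study coordinator will refer to the randomization scheme". On the method of allocation, section 2.3 says: "The randomization schedule will be generated by a biostatistician using simple random sampling". It describes no stratification. No section names the baseline CLDEQ-8 score as a covariate in any model.

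**The concern.** A change score assumes that the slope of week-8 score on baseline is exactly 1. Where the slope is lower, part of any chance difference in baseline score carries into the estimated effect, and the change score has more variance than it needs. ANCOVA estimates the slope instead.

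Two features make this relevant here. Allocation is simple and unstratified with 15 per arm, so chance imbalance in baseline score is a realistic prospect. Entry also requires a score of at least 12, so regression toward the mean is expected, by an amount that depends on each subject's baseline score.

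Neither later layer of section 5 secures the adjustment. The regression wording is illustrative, so baseline CLDEQ-8 might enter, but its only guide is whether the arms happen to differ. That settles the covariates after the data are seen and ignores known prognostic value. The longitudinal model does not constrain baseline means to be equal across arms, so it does not generally recover the ANCOVA gain.

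**Working it through.** **Inputs from section 3.3:** difference 3, change SDs 3.2 and 2.0, 15 per arm, two-sided 0.05. The baseline SD and the baseline-to-week-8 correlation are not given, so both are assumed below.

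**Step 1: the plan's figure.** Pooled SD = √((3.2² + 2.0²)/2) = 2.668 and d = 3/2.668 = 1.124. The noncentral t with 28 df gives 84.4%, as stated in Table 1.

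**Step 2: ANCOVA against change score.** Let k be the week-8 SD divided by the baseline SD, and r their correlation, both in the randomised sample.

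Var(ANCOVA)/Var(change) = k²(1 − r²)/(1 + k² − 2rk)

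This is multiplied by 27/26 for chance imbalance in the covariate. Power then uses 27 df, with the change SD held at 2.668.

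**Step 3: the entry cut-off.** Assume that baseline and week-8 scores are bivariate normal with equal SDs before selection, with correlation ρ. Let a = (12 − mean)/SD and λ = φ(a)/(1 − Φ(a)). After selection, in units of the pre-selection variance:

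- baseline variance v = 1 + aλ − λ²
- week-8 variance = ρ²v + 1 − ρ²

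Example with a = 0 and ρ = 0.5: v = 0.363 and week-8 variance = 0.25 × 0.363 + 0.75 = 0.841. So k = √(0.841/0.363) = 1.52 and r = 0.5/1.52 = 0.33. The variance ratio is 0.892, or 0.926 after the 27/26 factor, and power is 86.9%.

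| Pre-selection mean | v | ρ = 0.5: k, r, power | ρ = 0.7: k, r, power |
|---|---|---|---|
| 0.4 SD below 12 | 0.285 | 1.70, 0.29, 86.2% | 1.51, 0.46, 84.7% |
| at 12 | 0.363 | 1.52, 0.33, 86.9% | 1.38, 0.51, 85.2% |
| 0.4 SD above 12 | 0.460 | 1.37, 0.36, 87.8% | 1.26, 0.55, 85.7% |
| 0.8 SD above 12 | 0.571 | 1.25, 0.40, 88.8% | 1.18, 0.60, 86.3% |

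The gain over 84.4% is 0.3 to 4.4 points. Its median is about 1.8 points over ρ = 0.5, 0.6 and 0.7 at the four means. For scale, the t-test reaches 86.8% with 16 per arm and 88.8% with 17.

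**Step 4: wider assumptions.**
- With ρ from 0.3 to 0.8 under the same cut-off model, power is 84.1% to 91.5%. The low end is at ρ = 0.8 with the mean 0.4 SD below 12.
- On a grid that ignores the cut-off (r 0.3 to 0.9, k 1 to 1.5), power is 83.0% to 95.1%. The top needs equal SDs and r = 0.3 after selection, which the cut-off makes unlikely. The bottom, a loss of about 1.5 points, is at k = 1.25 and r = 0.8, where the slope kr = 1 and adjustment gains nothing.

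**Step 5: simulation** with truncated baselines, 60,000 trials per setting, the four means above and ρ = 0.5, 0.6 and 0.7. Power was 84.3% to 84.6% unadjusted and 84.6% to 89.0% with ANCOVA. Type I error was 4.8% to 5.2% and 4.9% to 5.2%. With arm-specific change SDs of 3.2 and 2.0, at three of the means and ρ = 0.5 and 0.7, ANCOVA power was 84.6% to 88.6% and type I error 5.0% to 5.3%.

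**Step 6: chance imbalance.** In the settings of the table the selected baseline SD is 1.57 to 2.69 points. One SD of the difference in mean baseline is √(2/15) = 0.365 times that, or 0.57 to 0.98 points. It moves the unadjusted effect by (1 − ρ) times that difference. For example, at ρ = 0.5 and mean 0.8 SD above 12: 0.5 × 0.365 × 2.13 = 0.39. The range is 0.21 to 0.39 points, and 0.43 to 0.78 for a two-SD imbalance, against a target difference of 3.

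**The case against.** The plan contains no error here. The change-score test is valid, matches the sample-size calculation and has the power claimed for it. The typical gain, about 1.8 points, is worth less than one extra subject per arm, and the figure of two applies only to the best setting in the table. The size rests wholly on assumed correlations and SDs. All of this stands, and it limits the weight of the point.

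Chance imbalance is also not a separate harm. Over repeated randomisations the test is unbiased, and baseline variation is already inside the change SD of 2.668. The standard error of the difference is 2.668 × 0.365 = 0.97 points, so a one-SD imbalance shifts the estimate by only about 0.2 to 0.4 standard errors. This also stands: imbalance and precision are largely two views of the same thing.

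Finally, section 5 would probably adjust for baseline CLDEQ-8 if the arms visibly differed on it. That softens the imbalance concern. It does not amount to prespecification, and it does not secure the precision gain when the arms look balanced.

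**Conclusion.** The point holds as a low-weight efficiency recommendation. The first-line primary test is unadjusted, and baseline CLDEQ-8 is not named as a covariate anywhere in the plan. The expected benefit of naming it is small: 0.3 to 4.4 points of power in the main settings, from a loss of 0.3 to a gain of about 7 points (91.5 − 84.4) if the pre-selection correlation is widened to 0.3 to 0.8. These figures rest on assumed bivariate normality before selection, equal pre-selection SDs and the stated range of means around 12. Confidence in the size is therefore medium, while the reading of the text is not in doubt. The change is worth making because it costs almost nothing and gives a covariate rule that does not depend on the observed balance.

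**What to change.** In section 5, state that the primary analysis is ANCOVA of week-8 CLDEQ-8 change on arm and baseline CLDEQ-8, whatever the observed balance. Remove observed difference between arms as a guide to choosing covariates, and name any further covariates in advance. Keep the t-test, the Wilcoxon test and the longitudinal models as sensitivity analyses. Because Wilcoxon is now the fallback for non-normal data, the same text should say that non-normality does not switch the primary method.

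The cost is one or two sentences and one degree of freedom, with no new data, visit or subject. The worst power loss found is 0.3 points in the cut-off settings and about 1.5 points on the broad grid. The sample-size calculation can stay as it is, since the unadjusted t-test figure is close to or below the ANCOVA power in the cut-off settings.

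### The only criterion named for choosing adjustment covariates is observed arm imbalance, which in a 30-person randomised trial picks chance differences rather than predictors of CLDEQ-8 change

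*Combined protocol and SAP*

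**What the plan says.** Section 5 (Statistics) first summarises baseline characteristics and looks at their balance between arms. For the primary outcome, "bivariate comparisons will be first conducted using t-tests", with a Wilcoxon test if the data are not normal. Multivariable regression comes next, for "adjustment of all other potential confounding variables such as baseline clinical and demographic characteristics that differ by study arms". For the longitudinal models offered as an alternative, the section adds: "All models will be adjusted for other clinical or demographic confounders".

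No covariate is named. No threshold for a difference between arms is given, and no limit on the number of covariates. The section does not say whether the unadjusted, adjusted or longitudinal result decides the trial.

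Section 3.3 gives power only for the unadjusted comparison: "we will achieve 84% power to detect a standardized mean difference of 1.12 between two groups of a size of 15 for each". No power is stated for any adjusted model.

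**The concern.** Section 2.3 allocates treatment by simple randomisation, so any baseline difference between arms is chance. It does not show that the variable predicts change in CLDEQ-8. A rule keyed to such differences selects variables because they correlate with arm. Those are the variables that widen the standard error of the arm effect, and nothing in the rule makes them explain outcome variance in return. It also means the adjusted model is settled only after the data by arm have been seen.

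Section 2.4 collects many baseline measures (acuity, osmolarity, staining, TBUT, Schirmer, slit-lamp grades, wearing time, drop use), and Section 5 adds demographics and lens modality. With 30 people, some of these will probably look unbalanced. At stake are the precision of the adjusted estimate, its dependence on which imbalances happen to arise, and the presence of two p-values for one question.

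**Working it through.** **Inputs from the documents (section 3.3).** Test and level: "using unpaired t-test in a two-sided hypothesis test with a significance level, 0.05". Size: "with the goal of randomizing 30 subjects (15 per arm"). Effect: "a difference of score change by 3 with standard deviations 3.2 and 2.0 for each group".

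**1. The plan's own figure.** Pooled SD = √((3.2² + 2.0²)/2) = √7.12 = 2.668, so d = 3/2.668 = 1.124. Noncentrality = d × √(15/2), with 28 df and critical t = 2.048.
- d = 1.12: noncentrality 3.067, power 84.1%.
- d = 1.124: noncentrality 3.079, power 84.4%.

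The stated 84% (84.4% in Table 1) is reproduced.

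**2. Cost of one covariate that just meets an imbalance test.** At p = 0.05, its correlation with arm is r = 2.048/√(2.048² + 28) = 0.361, so r² = 0.130. The variance of the arm effect is multiplied by 1/(1 − 0.130) = 1.15. If the covariate does not predict outcome, noncentrality = 3.067 × √(1 − 0.130) = 2.860 on 27 df, and power is 79%.

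For k such covariates, uncorrelated with each other, use 1 − k × r² and 28 − k df:
- two at p = 0.05: variance × 1.35, power 72%
- three at p = 0.05: variance × 1.64, power 63%
- three at p = 0.10 (r² = 0.094): variance × 1.39, power 71%

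**3. The rule over repeated trials.** The documents give neither the number of candidates nor a cut-off, so both are assumed. Simulation: 15 per arm, d = 1.12, independent normal candidates, each entered if its between-arm p-value falls below the cut-off, 4,000 trials per setting (Monte Carlo error about 0.6 point). Power of the adjusted model when no candidate predicts outcome:

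| Candidates | p<0.05 | p<0.10 | p<0.20 |
|---|---|---|---|
| 5 | 83% | 81% | 79% |
| 10 | 80% | 78% | 75% |
| 15 | 78% | 75% | 70% |

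Unadjusted power in the same runs was 84–85%. The chance that at least one of K candidates differs at p<0.05 is 1 − 0.95^K: 23%, 40% and 54% for K = 5, 10 and 15.

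**4. The same rule with prognostic candidates.** If the candidates jointly explain 30–50% of outcome variance, adjusted power is 73–86%. With 5 candidates it is 83–86%, essentially no loss. With 12 candidates, one correlated 0.5 with outcome and the rest 0.15, it is about 80–82%.

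**5. One covariate fixed in advance.** In 30 people the expected squared chance correlation with arm is 1/29. Noncentrality = 3.067 × √((1 − 1/29)/(1 − R²)) on 27 df, where R² is the assumed share of outcome variance explained.

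| R² | 0 | 10% | 20% | 30% | 40% | 50% |
|---|---|---|---|---|---|---|
| Power | 83% | 86% | 90% | 93% | 96% | 98% |

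**6. Two p-values.** With no true effect, the adjusted test alone rejected in about 3–6% of trials. With 12 candidates, the chance that either the unadjusted or the selected adjusted test is significant was about 5.5–7.5%.

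**The case against.** A reader might infer that the trial loses its planned power. It does not. The 84% is for the unadjusted t-test, which Section 5 runs first and which keeps that power whatever enters a later model.

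A reader might also infer a fall to about 60%. Figures of 60–72% do arise, but from entering all of 12 weak or unrelated candidates regardless of imbalance, which is a different policy. Under imbalance selection, values near 60% need about three strongly unbalanced covariates together, or a very loose cut-off.

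Nor do the documents support saying that adjustment always costs precision. Step 4 shows the loss can vanish. With one candidate correlated 0.5 with outcome and the rest 0.15, entering all 12 gives about 87%, slightly above the unadjusted test.

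The text is also looser than a strict selection rule. The arm differences are offered as an example of what to adjust for, and the longitudinal sentence has no imbalance criterion. So it is not established that a balanced, prognostic variable would be left out. Nor does Section 5 prescribe significance tests of baseline balance. The p-value cut-offs above are assumptions made to size the effect.

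What remains is that imbalance is the only criterion named, that it is the wrong one in a randomised trial, and that no list or limit constrains it.

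**Conclusion.** The point holds for the adjusted analyses only. The criterion stated is tied to chance association with arm, not to prognosis, so any gain in precision would be luck. Adjusted-model power of about 70–83%, against 84% unadjusted, rests on 5–15 independent, non-prognostic candidates and entry at p<0.05 to p<0.20. With strongly prognostic candidates the loss may be negligible. A covariate chosen in advance for prognosis gives about 86–98% if it explains 10–50% of outcome variance, and costs about one point (84% to 83%) if it explains none.

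The combined error of about 5.5–7.5% is a smaller, related matter. It arises because no single analysis is named as primary, and a better covariate rule alone would not remove it. The change is worth making because it costs almost nothing, not because the planned test is in danger.

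**What to change.** Replace both adjustment sentences in Section 5 with wording such as:

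> Adjusted analyses use a short fixed list of baseline covariates, including baseline CLDEQ-8, chosen before unmasking for their expected relation to CLDEQ-8 change and used whether or not the arms differ. Observed baseline differences are described and do not add covariates.

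Then add a separate sentence naming the one analysis that is primary for CLDEQ-8 change at week 8, with all others labelled supportive.

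Baseline CLDEQ-8 is already collected at Visit 1 (section 2.4), so no new data are needed. In any longitudinal model that keeps baseline as one of the response times, baseline CLDEQ-8 is already in the response, and only the rest of the list should enter as covariates.

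The cost is SAP wording, settled before unmasking. The downside is that a chance imbalance in an unlisted variable is shown but adjusted for only in a labelled sensitivity analysis.

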2.2 OVERALL DESIGN

This is a prospective, single site, randomized, double masked, comparator-controlled study designed to evaluate the efficacy of lifitegrast ophthalmic solution 5% in treating the symptoms of dry eye in soft contact lens wearers as compared to control. We hypothesize that there will be a significant improvement in dry eye symptoms in contact lens wearers using lifitegrast 5% as compared to those being treated with control (lifitegrast vehicle).

Potential study candidates will sign an informed consent form prior to any clinical procedures or tests specific to the protocol are performed. All screening examination procedures will be performed by the investigator or trained personnel working under the investigator's supervision. Subjects will undergo examination to determine eligibility at the Baseline visit. A complete medical, ocular and medication history will be obtained. Subjects who elect to participate will complete the study as outlined in Section 2.4. Signs and symptoms will be evaluated at baseline, 2 weeks, 4 weeks and 8 weeks. All tests and measurements will be obtained in accordance with the procedures specified in this protocol.

If found to be eligible, subjects will be randomized in a 1:1 ratio to either the test product (lifitegrast 5%) or control (lifitegrast vehicle) arm. Subjects will be instructed to use the drops twice a day in each eye. Drops are to be instilled in the morning at least 15 minutes before CL insertion, and after CL removal in the evening.

Subjects who are currently using reusable contact lenses will be required to use Clear Care solution to clean and disinfect their lenses.

Subjects will be asked to return to each visit with all of the used and unused vials dispensed at the prior visit. Subject accountability will be assessed at each follow up visit by comparing the amount of used vials to the amount of expected days of use. Trends in compliance will be considered during analysis of study data.

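### GEE is offered as an alternative analysis of the CLDEQ-8 score on about 30 participants with no small-sample correction named; with uncorrected robust errors the 5% test rejects about 7% of the time

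*Combined protocol and SAP*

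**What the plan says.** Section 5 first compares the arms on the 8-week change in CLDEQ-8 total score by t-test, or by Wilcoxon test if normality fails. Multivariable regression follows. It then continues: "Alternatively, we will use longitudinal linear models to analyze the difference of changes in total score between study arms", using the scores "across baseline, 2nd, 4th and 8th weeks". The methods in parentheses are mixed-effects models and "GEE with exchangeable and independent correlations". On covariates it says "All models will be adjusted for other clinical or demographic confounders", without listing them. The threshold is common to all analyses: "Two sided p-values <0.05 will be considered to be statistically significant".

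R is named as the software. No package, GEE variance estimator (model-based or robust), finite-sample correction or t or F reference is given. No rule says when the longitudinal analysis is used instead of the t-test, or which of the two working correlations is reported.

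Section 3.3 aims to randomize 30 participants, 15 per arm, and allows for screen failure but not for dropout. Section 2.2 says "subjects will be randomized in a 1:1 ratio". Section 2.3 says "The randomization schedule will be generated by a biostatistician using simple random sampling" and mentions no blocking, so the arm sizes can differ by chance.

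**The concern.** In this GEE each participant is one cluster. The ordinary sandwich variance is built from squared residuals of a model fitted to the same data. Those residuals are on average too small, and with 15 participants per arm the shortfall is not negligible. Referring the statistic to a normal distribution ignores the uncertainty in the variance estimate as well. Both effects make the test reject too often and the interval too narrow.

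At stake is the nominal level of an analysis that the plan may report on its primary score. A GEE p-value a little under 0.05 would be weaker evidence than it appears.

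**Working it through.** **The plan's own figure.** Section 3.3 states 84% power (84.4% in Table 1) for an unpaired t-test, 15 against 15, with a difference of 3 and SDs of 3.2 and 2.0. Pooled SD = √((3.2² + 2.0²)/2) = √7.12 = 2.668. Standardized difference = 3/2.668 = 1.124. Noncentrality = 1.124 × √(15/2) = 3.08. With 28 df the power is 84.4%, or 84.1% with the rounded 1.12, so the figure is reproduced. It concerns the t-test only. The plan states no operating characteristic for GEE.

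**Inputs from the plan:** 15 per arm, four visits (weeks 0, 2, 4 and 8), two-sided 0.05, exchangeable and independence working correlations. **Assumptions:** normal outcomes, the variance components, the number of completers, the number of covariates, and the use of the uncorrected sandwich with a normal reference.

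**Closed form, complete 15/15 data, no covariates.** With complete data at common visits, the arm contrast is a difference between two means of one summary per participant (a slope, or a change). The uncorrected sandwich divides each arm's sum of squares by n where the t-test divides by n-1. The robust statistic is therefore the pooled t statistic multiplied by √(15/14), and it passes 1.96 when |t| > 1.96 × √(14/15) = 1.894.

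- False-positive rate = P(|t₂₈| > 1.894) = **6.9%**. Under these conditions it does not depend on the within-participant correlation.
- Interval width relative to the exact t interval = 1.894/2.048 = 0.924, so it is about 7.6% too narrow.

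**Fewer completers or uneven arms** (same two-group contrast, uncorrected):

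| Arms | False-positive rate |
|---|---|
| 15/15 | 6.9% |
| 12/18 | 7.0% |
| 12/12 | 7.4% |
| 10/20 | 7.6% |
| 11/11 | 7.6% |
| 10/10 | 7.9% |

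**Simulated GEE under no effect.**

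- 24 scenarios with 30 participants, 10,000 trials each: linear time, categorical time, or a constant arm effect on change; exchangeable or independence; fixed 15/15 or simple randomization; no covariates. Range 6.5% to 7.7%. Monte Carlo SE = √(0.07 × 0.93/10,000) ≈ 0.3 points.
- Subject SD 3, slope SD 0.25 per week, residual SD 2 (all assumed), 3,000 trials per setting, arm-by-time test: 7.0% (independence) and 6.7% (exchangeable) at 15/15 with complete data; 7.3% to 8.2% at 12/18 with 15% dropout. Monte Carlo SE is about 0.5 points.
- A standard GEE routine, exchangeable, 2,500 trials at 15/15: 7.6%, SE about 0.5 points.

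**Covariates.** The arm-by-time slope contrast stays near 6.9% when between-participant covariates are added. In a model of change with a constant arm effect the rate is about 8% with two covariates, 10% with four and 11.5% to 12% with six. The plan lists no covariates, so these values show sensitivity only.

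**With a correction, 15/15 closed form.**

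- Uncorrected sandwich with t₂₈: P(|t₂₈| > 2.048 × √(14/15)) = 5.8%.
- Kauermann-Carroll type with t₂₈: P(|t₂₈| > 2.048) = 5.0%.
- Mancl-DeRouen type with a normal reference: P(|t₂₈| > 1.96 × √(15/14)) = 5.2%.
- Mancl-DeRouen type with t₂₈: P(|t₂₈| > 2.048 × √(15/14)) = 4.3%.

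In the GEE routine, Mancl-DeRouen gave 6.1% with a normal reference and 5.0% with t₂₈, so the t reference should accompany the correction. In the 3,000-trial settings, Mancl-DeRouen with t on n-2 df gave 4.1% to 4.9%.

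**The case against.** The strongest reply is that the plan never asks for uncorrected robust errors. It is silent, and an analyst could choose a corrected estimator without departing from it. That stands. A reader might infer that the plan itself fixes a 7 to 8% error rate; the documents do not support this, because the rate follows from an implementation choice that has not been stated.

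A reader might also infer that the primary comparison is compromised. It is not. The t-test or Wilcoxon test comes first, the sample size rests on the t-test, and neither uses a sandwich variance. GEE appears once, in parentheses, after the mixed model. However, the word that introduces the longitudinal models makes them an alternative, with no trigger and no label as a sensitivity analysis. The documents therefore do not exclude a GEE result being reported in place of the t-test.

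The size is also modest. The planned design sits near 7%, and values around 8% need dropout or imbalance. Simple randomization makes some imbalance likely: if each participant is assigned independently with probability one half, a split of 12/18 or worse occurs in about 36% of trials. The dropout rates are assumptions.

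Finally, a reader might conclude that GEE should be deleted in favour of a mixed model with Kenward-Roger or Satterthwaite degrees of freedom. That is a reasonable preference, but the working did not test that model, and a corrected GEE is enough to deal with the point.

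**Conclusion.** The point holds as a conditional one. An analysis allowed on the primary score at 0.05 lacks the specification it needs to hold that level with about 30 clusters. Under the usual uncorrected implementation the excess is about 2 percentage points for the planned 15/15 trial and up to about 3 under assumed attrition or imbalance, with intervals correspondingly too narrow. The closed form and the simulations agree on this.

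The result rests on normal outcomes and on the slope or change contrast without covariates. A constant-effect model with several covariates could be worse, but the plan does not say enough to put a figure on it. The point merits correction before unmasking. It does not call into question the comparison conducted first or the sample size.

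**What to change.** If GEE is kept, state in section 5:

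- one working correlation;
- a bias-corrected sandwich variance (Mancl-DeRouen or Kauermann-Carroll), with the R package named;
- a t reference on about n-2 degrees of freedom, n being the number of participants analysed;
- that GEE is supportive of the t-test or Wilcoxon comparison and does not replace it.

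This brings the false-positive rate to about 4 to 5% in the settings checked. The correction was not tested with covariates in the model, so the covariate list should be short and fixed in advance.

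The cost is a few lines of text and a software option, with no change to sample size, visits or data. The intervals become wider than the uncorrected ones: at 15/15 by a factor of 2.048/1.894 = 1.08 with Kauermann-Carroll and t₂₈, and 2.048 × √(15/14)/1.894 = 1.12 with Mancl-DeRouen and t₂₈. Mancl-DeRouen is slightly conservative at this size (4.3% in the closed form).
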